**Follow-up Visit:**

A follow-up visit will take place on C4/D29 in order to collect final safety assessments.

For details on all assessments please see the SOE in section [16.1](#).

For details on deuterated water administration and blood and sebum sampling for DNL assessments, please see section [9.1.17.5](#) De Novo Lipogenesis (DNL) Assessment.

**6.3 Rationale for Study Design and Endpoints**

This MAD study will assess the safety and tolerability, PK and preliminary PD of FT-4101 in overweight/obese subjects with NASH compared to placebo.

Two (2) cohorts will be assessed in ascending order, but may overlap, to determine the response to an intermittent dosing cycle (2 weeks of doing followed by 1 week off dosing).

Randomization is used to avoid bias introduced through an association between study drug allocation order and subject characteristics.

A double-blind design has been chosen to avoid bias and to maintain the blind between the administration of the study drug and placebo for subjects and clinical staff.

The placebo control group will control for changes in percent liver fat that may be caused by subjects' lifestyle and diet changes that may occur over the period of study participation.

Subjects with NASH will participate in the study, as these subjects are an important target population for FT-4101. Enrollment criteria will favor the target population. Percent liver fat will be determined by MRI-PDFF.

The proposed PK endpoints are well-established, commonly used parameters to characterize pharmacological profiles of drugs.

[figure not shown]
This is an exploratory study designed for proof of concept.

**6.4 Dose Escalation**

Data from at least 12 subjects of Cohort A who have completed 2 of the 4 cycles of treatment (2 week on /1 week off) is required for safety review before dose escalation to Cohort B, provided no more than one subject had an early discontinuation suspected of being related to FT-4101. The safety and tolerability data will be reviewed and if deemed appropriate by the Safety Review Committee (SRC) consisting of the coordinating PI, the Sponsor medical monitor and at least 1 additional participating center PI, a dose escalation decision to proceed to Cohort B will be made that is based on the reviewed data. If there are no safety concerns, the next cohort may start and may partially overlap with the previous one.

The blind of the study will be maintained throughout.

**Figure 6-2 Dose Escalation Schematic**

## **6.5 Study Discontinuation and Stopping Criteria**

### **6.5.1 Dose Escalation Stopping Criteria**

Dose escalation may be stopped if one of the following conditions applies:

- Death of a subject (AE grade 5 toxicity) in a cohort, at any time, that is considered related to the IP FT-4101 by the Investigator;
- Two (2) or more of the subjects in a cohort have experienced a serious adverse event (SAE) or medically significant adverse events (e.g., common terminology criteria for adverse events (CTCAE)  $\geq$  grade 3 may be used as a grading scale at the discretion of Investigator), that is judged by the Investigator to be possibly or probably related to the IP FT-4101;
- Two (2) or more subjects in a cohort develop an AE (CTCAE grade  $\geq$  2 may be used as a grading scale at the discretion of the Investigator) that persists for more than 7 days and is considered related to the IP FT-4101 by the Investigator;
- Two (2) or more FT-4101-treated subjects in a cohort develop an AE (CTCAE grade  $\geq$  2) of any duration associated with the skin (including hair) or eye that is considered to be at least possibly related by the Investigator;
- Two (2) or more subjects in a cohort develop similar clinically significant laboratory, significant ECG or vital signs abnormalities, or severe AEs in the same organ class, indicating dose-limiting intolerance. Dose escalation may proceed if after review of the data by the coordinating Investigator/medical monitor and discussion with Sponsor, it is concluded that the events are not related to the IP FT-4101;
- It is determined that the limit of safety and/or tolerability of FT-4101 has been reached. Decision will be made between Sponsor and Medical Monitor/coordinating Investigator.

### **6.5.2 Study Advancement after Dose Escalation Stopping Criteria**

After stopping criteria are met, the following may occur:

- Dose escalation may be stopped.
- Dose escalation may continue as originally planned. This is only permissible if the AE(s) that met stopping criteria is judged, after unblinded review, as not being related to FT-4101;
- A lower dose (lower than the dose that met stopping criteria) cohort may be added.

If the SRC decides on any action other than continuing dose escalation as planned, they will communicate to the Unblinded Statistician the subject numbers who they believe meet stopping criteria. The Unblinded Statistician will check the treatment assignment of that subject; if the subject received placebo then the stopping criteria are not triggered for that subject, otherwise the stopping criteria will be triggered. The Unblinded Statistician will communicate to the SRC their agreement that the stopping criteria are met after review of the treatment assignments, if applicable. If stopping criteria are not met due to events of concern occurring in placebo subjects, the Unblinded Statistician will communicate that the stopping criteria were not met, and communicate the subject numbers, who do not qualify based on receiving placebo. This unblinding will only occur in cases where the SRC has identified events potentially meeting stopping criteria, and will be limited only to subject numbers, experiencing the events in question. The whole cohort will not be unblinded to the SRC.

### **6.5.3 Criteria for Early Termination of the Study**

The study will be completed as planned unless one or more of the following criteria are satisfied that require temporary suspension or early termination of the study.

- New information or other evaluation regarding the safety or efficacy of the study medication that indicates a change in the known risk/benefit profile for the compound, such that the risk/benefit is no longer acceptable for subjects participating in the study.
- Significant violation of Good Clinical Practice (GCP) that compromises the ability to achieve the primary study objectives or compromises subject safety.
- Administrative Reasons, (e.g., Sponsor, an institutional review board (IRB)/ independent ethics committee (IEC), or regulatory authority elects to terminate or suspend the study or the participation of an investigational site)

If the Sponsor, IRB/IEC, or regulatory authority elects to terminate or suspend the study or the participation of an investigational site, a study-specific procedure for early termination or suspension will be provided by the Sponsor; the procedure will be followed by applicable investigational sites during the course of termination or study suspension.

#### **6.5.4 Criteria for Early Termination of Individual Subjects**

Subjects may withdraw their consent to participate in the study at any time.

If a subject withdraws consent, the date and reason for consent withdrawal should be documented. Subjects will be encouraged to remain in the clinic for safety assessments until the Investigator deems that it is safe for the subject to be discharged. Subject data will be included in the analysis up to the date of the consent withdrawal.

Criteria:

- AE or SAE that requires discontinuation at the discretion of the Investigator
- Protocol violation or concurrent illness: If protocol violation or concurrent illness occurs, which, in the clinical judgment of the Investigator or after discussion with the Sponsor, may invalidate the study by interfering pharmacokinetically or pharmacodynamically with the investigational products, the subject will be withdrawn by the Investigator (e.g., lack of compliance with study protocol, or lack of compliance with IP ingestion, as determined per Investigator)
- Lost to follow-up. The subject did not return to the clinic and attempts to contact the subject were unsuccessful. Attempts to contact the subject must be documented.
- Voluntary withdrawal of consent (mandatory removal from study)
- Discretion of Investigator (document reason on CRF)
- Subject becomes pregnant or begins breastfeeding (mandatory)
- Study discontinuation by Sponsor

Wherever possible, the tests and evaluations, including those listed for the Follow-up Visit should be performed for all subjects who discontinue prior to the completion of the study.

In the event the Investigator determines to terminate a subject participation in the Clinical Study, the Investigator must notify the Sponsor of such decision and rationale immediately in writing. In all cases, the appropriate IRB/IEC and other applicable regulatory authorities shall be informed.

#### **6.6 Treatment Interruption with Dose Modifications**

If a subject has an adverse event that is judged by the Investigator as related to study drug (i.e., assessed as unrelated to the underlying disease, intercurrent illness, or concomitant medications), then a treatment interruption with dose modification can be made according to the guidelines in [Table 6-1](#) below. Deviations from these guidelines (e.g., drug interruption for a Grade 1 AE of skin or eye) may occur if agreed upon by the Principal Investigator and Medical Monitor. There should be no attempt to make up doses omitted due to toxicity.

**Table 6-1 FT-4101 Recommended Treatment Interruptions and Dose Modifications for Adverse Events**

Severity of Adverse Events (AE)	Proposed Treatment Interruption and Dose Modification	
	Non-skin or eye	Skin or eye
Grade 1	Symptomatic treatment allowed: Continue FT-4101/placebo through treatment period. No dose modifications required.	Symptomatic treatment allowed: Continue FT-4101/placebo through treatment period. 
 
• If AE resolves < 7 days: continue FT-4101/placebo at same dose at next treatment cycle;
 
• If resolves <math>\geq</math> 7 days: dose reduction recommended at next treatment cycle;
 
• If AE not resolved at start of next treatment cycle, delay start of next treatment cycle for up to 7 days until resolution and dose reduce (discontinue study treatment if AE delay in next treatment > 7 days due to AE resolution).
 

Grade 2	Symptomatic treatment allowed: Continue FT-4101/placebo treatment through the treatment period.  If dose interruption is clinically indicated; 
 
• If resolved to baseline within 72 hours of treatment interruption, resume dosing at same dose level
 
• If resolved to baseline or Grade 1 > 72 hours of treatment interruption, dose reduce (or discontinue if prior dose reduction)
 
	Symptomatic treatment allowed: Dose interruption for the rest of treatment period required.  Resumption of a reduced dose of FT-4101/placebo at the start of the next treatment may be considered if the following are met: 
 
• Complete resolution of AE <math>\geq</math> 7 days before start of next treatment cycle
 
• No prior dose reduction
 
• Discussed and approved by Medical Monitor
 

Grade 3 or higher	Permanently discontinue treatment a	Permanently discontinue treatment

aException: In the setting of grade 3 nausea, vomiting, or diarrhea, hold treatment and if the subject is responsive to treatment measures within 72 hours, restarting FT-4101/placebo (at same dose or a reduced dose) may be considered after discussion with Medical Monitor.

Subjects are allowed one dose reduction in this study. Recommended dose reductions based on the subject's FT-4101/placebo starting dose are outlined in Table 6-2 below:

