## 7.2 Exclusion Criteria

Subjects who meet any of the following criteria at Screening will be excluded from the study:

1. Type 1 diabetes and type 2 diabetic subjects on insulin therapy.
2. Diabetic complications, such as history of acute proliferative retinopathy.
3. Recurrent severe hypoglycemia (more than 1 event  $\leq$  6 month) or hypoglycemic unawareness or recent severe ketoacidosis (hospitalization  $\leq$  6 month), as judged by the Investigator.
4. Subjects with a history of, or active, chronic liver disease due to alcohol, autoimmune, primary biliary cholangitis, HIV, HBV or active HCV-infection, Wilson's,  $\alpha$ -1-antitrypsin deficiency, hemochromatosis, etc., and not due to NASH disease.
5. Any history of clinically significant or decompensated chronic liver disease including esophageal varices, ascites, encephalopathy or any hospitalization for treatment of chronic liver disease; or MELD score  $\geq$  10.
6. History of significant cirrhosis of the liver or FibroSure®  $> 0.75$  at Screening (as shown on the laboratory report under Fibrosis Score).
7. Alcohol consumption greater than 14 drinks per week for men or greater than 7 drinks per week for women and/or positive alcohol breath test. (One drink is defined as 12 fluid ounces of regular beer (5% alcohol), 5 fluid ounces of wine (12% alcohol), or 1.5 fluid ounces of 80 proof (40% alcohol) distilled spirits.)
8. Introduction of an anti-obesity drug in the past 6 months prior to screening.
9. History of gastrointestinal malabsorptive bariatric surgery any other gastrointestinal surgery that may induce malabsorption, history of bowel resection  $> 20$  cm, any malabsorption disorder, severe gastroparesis, any GI procedure for weight loss (including LAP-BAND®), as well as clinically significant gastrointestinal disorders (e.g. peptic ulcers, severe gastrointestinal reflux disease [GERD]) within less than 5 years.
10. Ingestion of drugs known to produce hepatic steatosis including corticosteroids, high-dose estrogens, methotrexate, tetracycline or amiodarone in the previous 6 months.
11. Ingestion of drugs (as listed in the Table Prohibited Medication) from time points specified until completion of the study.
12. History of, or current cardiac dysrhythmias and/or a history of cardiovascular disease event, including congestive heart failure (class C and D of the American Heart Association [AHA]), unstable coronary artery disease, myocardial infarction.

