### 7.3 Study Restrictions/Precautions

#### 7.3.1 Prohibited Medications

Use of the agents listed below (prescription or nonprescription) is prohibited from the time points specified until completion of all study activities.

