**Table 7-1 Prohibited Medications**

Medication or Class	Indication/Reason	From time point specified until the end of the study
Antihypertensive medication	Hypertension	Excluded unless on stable dose for at least 3 months prior to screening
Statins	Hyperlipidemia	Excluded unless on stable dose for at least 3 months prior to screening
Oral or systemic long-acting corticosteroids	E.g., chronic or acute non-infectious inflammatory conditions, auto-immune diseases	Within 3 months prior to screening
Antacids, anticholinergics, antispasmodics (e.g., modafinil, phenytoin), 5HT3 antagonists, dopamine antagonists, or opiates, antiemetics	Reduction/modification of GI motility	Within 2 weeks prior to screening
Orlistat, lorcaserin, sibutramine, etc., including over-the-counter and herbal supplements, or any medication with a labelled indication for weight loss or gain	Weight control treatment	Within 3 months prior to screening.

Medication that is a strong inducer or strong inhibitor of CYP3A4  Please see Appendix C in section 16.3 .	Interaction with CYP3A4	Within 15 days prior to dosing, unless half-life is greater than 72 hours, then it is prohibited for 5 half-lives prior to dosing.
--	-------------------------	--

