### 7.3.2 Check-in Criteria

At check-in for any in-house period(s), a subject will not be allowed to check in if they meet any of the following criteria and the treatment period may be rescheduled one time. The Sponsor will be notified about the rescheduling in a timely manner.

1. Positive alcohol breath test.
2. Positive urine drug screen test.
3. Positive urine pregnancy test in female subjects. If sample is positive, blood sample will be sent to local lab for confirmation. A negative test result is mandatory prior to dosing.
4. Any medical condition that could interfere with the study, as judged by the Investigator.
5. Any use of disallowed concomitant medications within the last 24 hours.
6. Consumption of grapefruit (grapefruit containing food and beverages), star fruit (carambola), pomegranate, Seville orange and other food components that may interact with CYP3A4, within 24 hours prior to check-in.

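### Table 6-1 allows nausea and vomiting to be treated and ties a restart to 72-hour response, but Table 7-1 bans all antiemetics to study end, so giving one is a protocol deviation

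*Protocol*

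**What the plan says.** **Managing the event (Protocol 6.6 and Table 6-1).** The table applies to an adverse event "judged by the Investigator as related to study drug". For Grade 1 and Grade 2 events outside skin and eye it allows symptomatic treatment and continues study drug. If a Grade 2 event needs an interruption, the clock matters: "If resolved to baseline within 72 hours of treatment interruption, resume dosing at same dose level". If resolution takes longer than 72 hours, the table recommends a dose reduction, or discontinuation where the dose was reduced before. Grade 3 or higher means permanent discontinuation, with one exception in footnote a: "In the setting of grade 3 nausea, vomiting, or diarrhea, hold treatment and if the subject is responsive to treatment measures within 72 hours", a restart at the same or a reduced dose may be considered after discussion with the Medical Monitor.

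**Drugs that may be used (Protocol 7.3.1 and Table 7-1).** The row on drugs that alter GI motility includes "5HT3 antagonists, dopamine antagonists, or opiates, antiemetics". Its ban starts two weeks before screening. Under section 7.3.1 the listed agents, prescription or not, are "prohibited from the time points specified until completion of all study activities". Exclusion criterion 11 repeats this: "Ingestion of drugs (as listed in the Table Prohibited Medication) from time points specified until completion of the study".

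**Check-in (Protocol 7.3.2).** A subject may not check in to an in-house period after "Any use of disallowed concomitant medications within the last 24 hours". Section 9.1.12 carries the same bar and allows one reschedule.

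**The concern.** One table invites treatment of nausea and vomiting and makes a dosing decision depend on the response. The other prohibits the drug class defined by treating those symptoms. An investigator who follows the text must manage with something other than an antiemetic, or give one and record a deviation.

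Two things are at stake. The first is subject care: ordinary treatment of a foreseeable symptom is labelled a departure from protocol. The second is exposure to study drug: slower recovery can carry a subject past the 72-hour mark, where the recommended action is a reduced dose or discontinuation. Under the present text, an antiemetic taken in the 24 hours before C4/D14 also bars check-in to that visit.

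**Working it through.** No power or error-rate figure is involved. The check is whether any part of the protocol permits an antiemetic for an adverse event, and how long the ban lasts.

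**Search for an exception**

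| Place | What it offers | Does it permit an antiemetic? |
|---|---|---|
| Table 6-1 | Symptomatic treatment; treatment measures | Names no drug, so it does not override Table 7-1 |
| Table 7-1, GI-motility row | A start point only | No. Three of the six rows (antihypertensives, statins, strong CYP3A4 agents) carry an 'unless' clause; this one does not |
| Section 6.6 | Principal Investigator and Medical Monitor may agree to depart from the guidelines | Covers the Table 6-1 guidelines only, and only related events |
| Section 9.1.7 | Recording and notification of concomitant therapy | No; it refers back to Table 7-1 |
| Section 13.2 | Departure for an immediate hazard, or after contact with the medical monitor and Sponsor, with prior contact waived for emergency or immediate need | Treatment can be given, but it remains a documented deviation |

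No section turns antiemetic use for an adverse event into permitted use.

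**Length of the ban after first dose** (nominal 21-day cycles, Protocol 6.1 and Appendix A)

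- C4/D1 = 3 × 21 + 1 = day 64.
- C4/D14 = 64 + 13 = day 77.
- C4/D29 = 64 + 28 = day 92 (90 to 94 with the follow-up window of 2 days either side).
- Dosing days = 4 × 14 = 56.

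**Reach of the check-in bar after first dose.** There is one in-house check-in, at C4/D14, with a 24-hour look-back: about 1/92 = 1.1% of days.

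**PK samples at that visit** (Protocol Appendix B). C1/D1 has 5; C1/D15, C2/D1, C2/D15, C3/D15, C4/D4 and C4/D8 have 1 each, so 6; C4/D14 has 8; C4/D15 has 2. The total is 5 + 6 + 8 + 2 = 21, of which C4/D14-15 holds 8 + 2 = 10, or 48%.

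These counts describe the length of the ban and the content of one visit. They do not say how often the conflict would arise. Protocol sections 4.3 and 7.3.3.1 name skin, eye and hair effects and no GI event.

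**The case against.** The best reply is that the tables do not contradict each other. Table 6-1 names no drug, Table 7-1 is the specific rule on drugs, and non-drug or unlisted measures satisfy both. The row also states its purpose, the effect on GI motility, which makes sense for an oral drug with Cmax, Tmax and AUCtau as secondary endpoints. This stands as far as it goes: Table 6-1 can be followed. It explains a default ban, but not why the ban is silent on treating an event for which the sponsor wrote its own restart rule.

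A reader might infer that the investigator is forced to withhold care. The documents do not support that. Section 13.2 already gives an emergency route and a managed route to an antiemetic. What remains is that each use is a deviation.

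A reader might also infer that slow recovery must cost study drug. That goes too far. Table 6-1 is headed as recommended and section 6.6 calls it guidelines. At Grade 2 the first instruction is to continue, and for related events the Principal Investigator and Medical Monitor may agree to a different course. Nor is withdrawal automatic after a deviation: section 6.5.4 requires a judgement that it may invalidate the study through PK or PD interference.

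Finally, the check-in bar might look like a separate defect that needs its own edit. It does not. It reaches only disallowed medication, so it falls away once Table 7-1 permits the drug. The bar on "Any medical condition that could interfere with the study, as judged by the Investigator" still covers a subject who is unwell.

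**Conclusion.** The point holds as a minor inconsistency between two protocol rules. Symptomatic treatment is allowed at Grades 1 and 2, and a possible restart after Grade 3 nausea or vomiting depends on response to treatment. Yet antiemetics are prohibited as a class to study end, and their use for an adverse event is a deviation by whatever route it is reached. Followed as written, the rule gives somewhat worse care or a needless deviation, and may lead to a recommended dose reduction or discontinuation that faster recovery would have avoided.

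The size cannot be expressed as a rate, because the documents give no expected frequency of nausea or vomiting. It would be wrong to read this as a threat to the liver-fat comparison: nothing in the documents supports such an effect and none is claimed. The point is confined to antiemetics for nausea or vomiting. Footnote a also names diarrhea, but no conclusion is drawn about its treatment. The day counts assume nominal cycles without delays.

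**What to change.** Add one footnote to the GI-motility row of Table 7-1:

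'After the first dose of IP, short-term use of an antiemetic (including a 5HT3 or dopamine antagonist given as one) to treat an on-study AE of nausea or vomiting is permitted with Medical Monitor agreement (beforehand where feasible, otherwise within 24 hours); drug, dose and times are recorded; strong CYP3A4 inhibitors and inducers remain prohibited.'

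Exclusion criterion 11 refers to the table and needs no edit; nor do sections 7.3.2 and 9.1.12.

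The cost is one footnote, with no new visits, samples or subjects. The downside is that a motility-modifying drug may occasionally be present in a C4/D14-15 PK profile. Whether that profile is evaluable is decided under SAP 4.3, in the analysis-set memo that SAP section 4 already requires before database lock, so the SAP does not change.
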